7.1.6 Severity Definitions

- **Mild:** Subject awareness of a sign or symptom that is easily tolerated, requires no treatment, and does not interfere with subject's daily activities.

- **Moderate:** Subject awareness of a sign or symptom which may be a low level of concern to the subject and may interfere with daily activities but can be relieved by simple therapeutic care.
- **Severe:** A sign or symptom that interrupts the subject's daily activity and requires systemic therapy or other treatment

7.2 Procedures for Evaluating Adverse Events

Throughout the course of this study all efforts will be made to remain alert to reportable AEs. If an AE occurs the first concern will be the safety of the subject and appropriate medical intervention will be made. All SAEs, ocular and systemic, must be recorded and reported as required.

All reportable AEs occurring after signing of informed consent and through the subject's end of participation in the study must be reported. All reportable AEs must be followed until the event resolves or stabilizes. This may imply that follow-up will continue after the subject has left the study, and that additional evaluations may be requested by the Sponsor.

Ocular AEs of possible clinical significance should be photo-documented and shared with the Medical Monitor in electronic form.

When evaluating for reportable AEs, the Investigator should refer to the definitions for AEs to determine:

- Whether the event is serious (refer to [Section 7.1.1](#) and [Section 7.1.2](#))
- Whether the event is severe (refer to [Section 7.1.6](#))
- Whether the event is significant (refer to [Section 7.1.2](#) and [Section 7.1.3](#))
- Whether the event is related to the study device (refer to [Section 7.1.5](#))

7.3 Procedures for Reporting Adverse Events

7.3.1 Procedures for Reporting Serious or Significant Adverse Events

An AE classified as a SAE or a Significant Non-Serious Ocular AE requires expeditious handling and reporting to the Sponsor to comply with regulatory requirements, as follows:

- To ensure subject safety, all SAEs, regardless of relationship to the study device, must be immediately (i.e., within a maximum 24 HOURS after becoming aware of the event) reported to [REDACTED] and Sponsor. All information relevant to the SAE must be recorded on the Sponsor provided SAE report form signed by the Investigator. Within 24 hours of knowledge of a new SAE, the Investigator must enter the SAE information onto the hard copy SAE report form and send the form to the following email distribution:
 - [REDACTED]
- The Investigator must verify that the report was received by MedTrials and/or the Sponsor. If the Investigator is not able to verify it was successfully received by

[REDACTED] and/or Sponsor, the Investigator must call the CRO clinical study manager by phone to follow-up. The CRO will forward the documentation to the medical monitor and the sponsor for review.

- Investigators should not wait to receive additional information to fully document the event before initially notifying [REDACTED] and Sponsor of an SAE or a Significant Non-Serious AE. Additional relevant information such as hospital records and autopsy reports should be provided to [REDACTED] and Sponsor as soon as they are available.
- The Investigator should take all appropriate measures to ensure the safety of the subjects: notably, he/she should follow a subject with an SAE or Significant Non-Serious AE until the event has resolved or the condition has stabilized. This may imply that follow-up will continue after the subject has left the study, and that additional evaluations may be requested by the Sponsor.
- Ensure that the subject's identity is protected and the subject's identifiers in the clinical trial are properly mentioned on the form.
- BEGIN TREATMENT OF THE AE IMMEDIATELY BY A SUITABLY LICENSED EYE CARE PROFESSIONAL.
- Continue to update the paper SAE or Significant Non-Serious AE Report Form, if applicable, each time the subject is seen during the management of the event and at resolution of the event. All updated report forms should be submitted by the site to [REDACTED] and the Sponsor within 24 hours. Whenever possible, it is suggested that the Investigator take photographs of all ocular AEs of possible clinical significance and forward them to [REDACTED] and the Sponsor.
- Events requiring medical treatment will be evaluated by the Sponsor. Upon review of the medical treatment, Bausch + Lomb Clinical Operations representatives may contact the Investigator to request further information concerning the treatment.
- Report all USADEs to the reviewing IRB within 10 working days following awareness of the USADE or according to the established reporting procedures of the IRB, whichever is shorter.
- Submit all bills, prescription receipts, and culture reports/fees related to the AE to the Bausch + Lomb Clinical Operations. Expense incurred for study related medical treatment will be paid by Bausch + Lomb Clinical Operations.

7.3.2 Procedures for Reporting Off-Site Unanticipated Serious Adverse Device Effects

When participating in multicenter clinical investigations, Investigators may receive off-site USADE reports. These are Sponsor reports of USADEs which occurred at other clinical sites for the same trial, or in different trials using the same investigational test article or comparator, that met the criteria for reporting to a regulatory agency. These should be reported to the reviewing IRB within 10 working days or per their established reporting procedures, whichever is shorter.

7.3.3 Device Deficiencies: Definition and Reporting Procedures

A device deficiency is defined as an inadequacy of a medical device with respect to its identity, quality, durability, reliability, safety, or performance. Device deficiencies include malfunctions, use errors, and inadequate labeling.

Investigators must evaluate, record, and report any complaints/deficiencies or malfunctions experienced with the study lens during this trial to the Medical Monitor promptly using the Device Deficiency Report and provide all source documents and eCRFs that will assist with evaluation of risk to subject safety (e.g. symptoms/complaints, lens performance ratings, VA, topography, mire reflex, slit lamp, etc.). The Sponsor and Medical Monitor shall review all device deficiencies, and, upon the Sponsor's request, Investigators must supply any additional information related to the safety reporting of a particular event.

Report device deficiencies **within 24 hours** of knowledge to:

- [REDACTED]

The Medical Monitor will distribute, within 24 hours of knowledge, all device deficiencies to the Sponsor.

The Sponsor shall review all device deficiencies and determine and document in writing whether they could have led to an SAE. In the event of a disagreement between the Sponsor and the Investigator(s), the Sponsor shall communicate both opinions to the reviewing IRB per their established reporting procedures and the health authority.

7.3.4 Procedures for Reporting and Culturing of Corneal Ulcer or Suspected Ocular Infection

For purposes of this study, the Sponsor requests that cultures should be obtained in cases of corneal ulcer or suspected ocular infection, unless medically contraindicated. Cultures should be taken from the cul-de-sac, lower eyelid margin, and the corneal lesion (if applicable). The required culturing techniques are outlined in [Appendix B](#).

When a culture is obtained, the contact lenses and contact lens cases which were being utilized by the subject at the time of the AE should be collected from the subject for culturing and processing by the local clinical laboratory designated by the site.

Microbial data generated from returned subject supplies (e.g., lenses, lens cases, and/or lens case solutions) are for information only. Because microbes may be introduced into subject supplies during use, recovery of microbes from returned subject supplies cannot be presumed to indicate etiology or direction of organism transmission.

The ocular cultures, along with the associated contact lenses and contact lens cases, will be sent to the local clinical laboratory designated by the site for analysis. The clinical laboratory will report the culture results to the Investigator who will record the results in the eCRF.

7.3.5 Guidelines for Reporting Pregnancies

During the study, all female subjects of childbearing potential should be instructed to contact the Investigator immediately if they suspect they might be pregnant (e.g., missed, or late menstrual period). Female subjects who become pregnant during the study will be

followed until completion of pregnancy. Every effort will be made to obtain the health status of the mother and infant or fetus (in cases of miscarriage or therapeutic abortion) at term. Pregnancy itself is not considered an AE.

All confirmed pregnancies must be reported on a Pregnancy Report and submitted to the Medical Monitor via facsimile or email transmission within 24 hours of the Investigator's awareness of the pregnancy. The Medical Monitor will distribute the completed report to the Sponsor as per the distribution listed below.

All pregnancies will be followed until outcome even after study closure. The outcome of all pregnancies will be reported on a paper Pregnancy Outcome Report and submitted to the Medical Monitor via facsimile or email transmission once the outcome is learned. The Medical Monitor will distribute the completed report to the Sponsor as per the distribution listed below.

Although pregnancy occurring in a clinical study is not considered to be an AE or SAE, any pregnancy complication, spontaneous abortion, or elective termination of a pregnancy, for medical reasons, will be recorded as an SAE. Any serious complication or event resulting from the pregnancy should be reported to the Medical Monitor within 24 hours on the SAE or Significant Non-Serious AE Report Form along with the Pregnancy Report Form.

The contact for reporting pregnancies and pregnancy outcomes are:

○ [REDACTED]

7. STATISTICAL METHODS

Changes to these statistical plans will be documented in protocol amendments and/or the statistical analysis plan.

8.1 Study Endpoints

8.1.1 Primary Safety Outcomes

The primary safety outcome is the rate of serious adverse events at the subject and eye levels.

[REDACTED]

[REDACTED]

[REDACTED]

[REDACTED]

[REDACTED]

8.1.3 Primary Effectiveness Outcomes

The primary effectiveness outcome is the proportion of subjects who achieve high-contrast monocular UDVA of 20/40 or better in both eyes at the 3-Month Follow-up Visit.

8.2 Hypotheses

No statistical hypotheses will be tested.

8.3 Sample Size

The FDA recommended a sample size of 50 completed subjects. The sample size is not based on statistical hypothesis tests. Enrollment of 70 subjects will allow for early discontinuation of up to 28% of the subjects to achieve a final sample size of 50 subjects.

8.4 Randomization

There will be no randomization in this single treatment study.

8.5 Study Populations

8.5.1 Full Analysis Set (FAS)

The FAS will consist of all dispensed subjects for subject level summaries and, for eye level summaries, both of their eyes.

8.5.2 Per Protocol (PP) Set

The PP Set will consist of all FAS subjects without important protocol deviations that could affect the primary effectiveness endpoint. The membership of the PP Set will be determined prior to database lock.

8.5.3 Safety Set

The FAS will be used to evaluate safety outcomes.

8.6 Statistical Analysis

8.6.1 Methods of Analysis

General Methods

Continuous data will be summarized using sample size (n), mean, standard deviation (SD), median, minimum, and maximum. Categorical data will be presented using the total counts for each category and corresponding percentages. The denominator for each percentage will be the number of subjects or eyes with non-missing data unless otherwise indicated.

Data from the FAS will be used for analysis unless otherwise specified.

For each assessment, the baseline value will be defined as the last observation before the first insertion of the study lenses. Change from baseline will be computed as follow-up value minus baseline value.

As customary for contact lens trials, eyes will be treated as independent sampling units in eye level analyses unless otherwise noted.

Listings of data will be produced in addition to tables of summary statistics.

The proportion of subjects with non-missing monocular UDVA data for both eyes at the 3-Month Visit who achieved monocular UDVA of 20/40 or better in both eyes at the 3-Month Follow-up Visit will be presented.

As a sensitivity analysis, the summary will be produced using the PP Set.

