3.3.3 Subject Discontinuation

A subject MAY be discontinued (at the discretion of the Investigator, the Sponsor, and/or the IRB) prior to the final study visit for a variety of reasons, including, but not limited to:

1. An adverse event (AE) occurring during the course of the study, which precludes continued treatment or follow-up
2. Persistent Grade 3 or 4 slit lamp findings (must be reported to the Sponsor within 24 hours)
3. Persistent study-related symptoms/complaints

A subject MUST be discontinued prior to the final study visit for any of the following reasons:

1. Voluntary withdrawal
2. Death
3. Investigator decision that it is not in the best medical interest of the subject to continue participation in the investigation
4. Ineligible at Screening Visit – a subject who was enrolled but was later found to have not met the eligibility criteria
5. Inability to maintain recommended wearing schedule
6. Continued failure to follow subject instructions
7. Lack of motivation
8. Lost to follow-up (refer to [Section 3.3.4](#))
9. Misses the Dispensing, 1-Day, or 1-Week Visit
10. Misses more than one of the 1-Month, 2-Month or 3-Month Visits
11. Instillation of non-medically indicated solution not specified in the protocol
12. Unacceptable lens performance
13. Becomes pregnant during the study

Prior to discontinuing a subject, every effort should be made to contact the subject, schedule a final study visit, obtain as much follow-up data as possible, and retrieve all study materials. Adverse events will be followed as described in [Section 6.1.12](#).

Subject discontinuations will be documented clearly on the source document and applicable electronic case report form (eCRF). The Investigator should indicate the PRIMARY (one) reason that the subject was discontinued for each eye. Subjects who voluntarily withdraw from the study are not required to provide a reason for their decision but should be encouraged to share this information.

Exit Visit assessments should be completed for early discontinued subjects, if possible.

At the final study visit, all study subjects should be examined to ensure that their ocular health is consistent with pre-study, baseline conditions. Any adverse effects determined to have been reasonably caused by participation in the study will be followed per the

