- i. Collect/assess all AEs/ADEs, including serious or significant non-serious AEs.
- j. Remind the subject that it is recommended that the lenses be worn overnight for at least eight (8) hours each night.

- k. If the lens fit is unacceptable, order two lenses if refitting one eye (or two pairs of lenses if refitting both eyes) by following the instructions for lens refitting in the Lens Order Instructions Form. New lens(es) will be made and sent to the Investigator for dispensing. The subject should suspend wearing study lenses while the new lens(es) are being made.

Upon receipt of the new lens(es) schedule an Unscheduled Visit due to refinement of lens fit and reset the sequence of follow-up visits on a subject basis starting with the 1-Day Follow-up Visit followed by a 1-Week Follow-up Visit, etc.

Note: If the lens fit is not acceptable, refinement to the lens can be made at this visit only if a lens refit was not ordered at the 1-Day Follow-up Visit.

- l. Schedule the subject to return for 1-Month Follow-up Visit within 2 hours of the subject removing the lenses.
 - m. Complete the relevant Follow-up Visit eCRFs.

6.1.5 1-Month Follow-Up (Visit 5)

The subject must return for the 1-Month Follow-up Visit on day 30 (\pm 3 days).

- a. Record any changes in concomitant ocular medications.
- b. Collect the following lens wear parameters:
 - Hours since lens removal
 - Average number of nights per week worn
 - Average nightly wearing time, hours per night
 - Frequency of rewetting drops use

Note: At the 1-Month Follow-up Visit no additional refinement can be made to the lens design. If the lens performance is acceptable, continue with the scheduled visits. If the lens performance is unacceptable, subject should be discontinued.

Note: Do not perform any ophthalmic examinations with the maintenance lenses in place (if any).

- c. Collect Symptoms/Complaints.
- d. Collect Lens Performance ratings using 0-100 scales.
- e. Perform uncorrected high-contrast distance visual acuity (UDVA) for each eye.
- f. Perform the following assessments (without lenses) using a phoropter:
 - Spherocylindrical refraction. Explain any induced refractive astigmatism greater than 1.00D compared to the Dispensing Visit (Visit 2).
 - Distance high-contrast BSCVA. Explain any loss of BSCVA of 2 or more lines compared to the Dispensing Visit (Visit 2).
- g. Perform corneal topography and record:
 - Topography reading
 - Mire reflex

- Keratometry readings

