8.6.8 Missing Data

Missing data will not be imputed.

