 - Ensure that the subject arrives for their appointment wearing the study lenses.
- 1-Week Follow-up Visit
- 1-Month Follow-up Visit
- 2-Month Follow-up Visit
- 3-Month Follow-up Visit

5. Maintenance Lenses

Daily disposable soft contact lenses (Bausch + Lomb Biotrue ONEday (nesofilcon A) Contact Lenses, known as “maintenance lenses”) will be dispensed at the 1-Day Follow-up Visit as needed to provide supplemental visual correction during the day as needed for the orthokeratology lens adaptation period.

Although the majority of subjects may not require maintenance lenses, Bausch + Lomb will provide each investigative site a supply of Bausch + Lomb Biotrue ONEday (nesofilcon A) Contact Lenses in representative powers of -0.50, -1.00, -1.50, -2.00, -2.50, and -3.00D for use as needed during the orthokeratology lens adaptation phase.

6. To Refine Lens Fit

Note: Each eye can only be refit one time, either at the 1-Day Follow-up Visit or the 1-Week Follow-up Visit.

If the lens fit is unacceptable, order two lenses if refitting one eye (or two pairs of lenses if re-fitting both eyes) by following the instructions for lens refitting in the Lens Order Instructions Form.

The following information will be required for lens refitting:

- Subject ID (6 digit):
- Investigator Name:
- Account ID: 0ARISE
- Category: Refitting
- Topography map file for OD and/or OS, taken after overnight wear of previously dispensed study lenses

- File should be sent pre-populated with:
 - Subject ID (first name = type the word “SUBJECT”, last name = 6-digit subject ID)
 - Subject date of birth
 - Subject spectacle refraction.
- Reason for refitting (indicate either OD or OS, if only applies to one):
 - Lens is Vaulting
 - Lens is riding High
 - Lens is riding Low
 - Lens has Lateral Displacement
 - Undercorrection or overcorrection of treatment with the following refraction data (without lens):
 - OD/OS sphere, cylinder, axis, visual acuity
 - Other reason(s) – please specify, e.g., lens discomfort

7. Patient Education

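### The primary effectiveness rate covers only subjects with 3-Month UDVA in both eyes, so it may differ from the all-dispensed rate, and the visible plan reports no bounds on the difference

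*Combined protocol and SAP*

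**What the plan says.** Section 8.1.3 defines the primary effectiveness outcome as "the proportion of subjects who achieve high-contrast monocular UDVA of 20/40 or better in both eyes at the 3-Month Follow-up Visit". It sets no condition on data being present. Section 8.6.1 makes the FAS the default analysis set, and Section 8.5.1 defines it: "The FAS will consist of all dispensed subjects for subject level summaries".

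For the primary summary, Section 8.6.1 narrows the denominator: "The proportion of subjects with non-missing monocular UDVA data for both eyes at the 3-Month Visit who achieved" the acuity criterion in both eyes. The same section also bases percentages in general on non-missing data unless otherwise indicated. Section 8.6.8 adds: "Missing data will not be imputed". The one visible sensitivity analysis repeats the summary in the Per Protocol (PP) Set, which Section 8.5.2 forms from FAS subjects without important deviations.

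Three features of conduct affect who has 3-Month data:

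- Section 3.3.3 lists "Unacceptable lens performance" among the reasons for mandatory discontinuation. Section 6.1.5 (1-Month visit) says: "If the lens performance is unacceptable, subject should be discontinued".
- Under Sections 3.3.3 and 6.1.10, missing only one of the 1-, 2- and 3-Month visits does not force discontinuation. A subject can therefore stay in the study and still have no 3-Month value.
- Exit Visit assessments are requested from early discontinuations where possible (Section 3.3.3). They include UDVA in each eye (Section 6.1.8), but Section 8.6.1 gives them no role in the primary summary.

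**The concern.** The trial has one arm, no comparator and no hypothesis test, so this proportion is its main effectiveness result. A reader will naturally take it as the success rate among people given the lens. As specified, it is the success rate among those who reached 3 months with both eyes measured.

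The two rates agree only if the subjects without data would have succeeded as often as those with data. The protocol gives a reason to doubt that, because one route out of the denominator is discontinuation for poor lens performance. Some of those subjects are plausible acuity failures, and they leave both numerator and denominator. The PP analysis can only remove further subjects, and nothing lifts the non-missing rule for it, so it cannot show the effect of this loss.

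There is also a smaller logical gap. A subject with one eye observed worse than 20/40 at 3 months has already failed a both-eyes endpoint. If the fellow eye is missing, Section 8.6.1 drops that subject instead of counting the failure.

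**Working it through.** **The plan's own figure.** Section 8.3 aims for 50 completed subjects and allows up to 28% early discontinuation. 50 / (1 − 0.28) = 69.4, rounded up to 70, which matches the stated enrolment of 70. Losing 20 of 70 is 28.6%. This allowance runs from enrolment, so loss after dispensing may be smaller.

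**Formulas.** Let N be subjects dispensed, n those with 3-Month UDVA in both eyes, and r the successes among them.

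- Evaluable-only rate: r / n
- Worst case over all dispensed (all missing fail): r / N
- Best case (all missing succeed): (r + N − n) / N

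If m = (N − n)/N is the missing share, p = r/n, and q is the unknown success rate among the missing, the all-dispensed rate is (1 − m)p + mq. The evaluable-only rate therefore exceeds it by m(p − q). The excess is positive only when q is below p. It lies between −m(1 − p) and mp.

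**Inputs.** The documents give neither a success rate nor a count of losses after dispensing. All counts below are assumptions, chosen for evaluable rates near 90%.

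| Dispensed N | Evaluable n | Successes r | Missing share | Evaluable-only | Worst case | Best case | Evaluable minus all-dispensed |
|---|---|---|---|---|---|---|---|
| 90 | 81 | 73 | 9/90 = 10.0% | 73/81 = 90.1% | 73/90 = 81.1% | 82/90 = 91.1% | +9.0 to −1.0 points |
| 60 | 50 | 45 | 10/60 = 16.7% | 45/50 = 90.0% | 45/60 = 75.0% | 55/60 = 91.7% | +15.0 to −1.7 points |
| 70 | 50 | 45 | 20/70 = 28.6% | 45/50 = 90.0% | 45/70 = 64.3% | 65/70 = 92.9% | +25.7 to −2.9 points |

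The last row applies the whole Section 8.3 allowance to dispensed subjects, so it illustrates heavy loss and is not a forecast.

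**One-eye case.** Add one subject with an observed failing eye and a missing fellow eye to 45/50. The rate becomes 45/51 = 88.2%, a change of 1.8 points. Both eyes are due for measurement at the same visit (Section 6.1.7), so few such subjects are expected.

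Separately, Section 8.3 works from 70 enrolled while the Synopsis and Section 3.1 give about 90. These need reconciling, but the point here does not depend on which applies.

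**The case against.** The strongest reply is that this is a disclosed, ordinary choice. An outcome at a visit needs an observation at that visit. Section 8.6.1 states the non-missing denominator both as a general rule and for this proportion, and Section 8.3 sizes the study on completers. The analysis is descriptive (Section 8.2), and no success threshold is visible that the choice could help to meet. Counts accompany percentages, listings are produced, discontinuation reasons are summarised for the FAS (Section 8.6.4) and baseline tables cover the FAS (Section 8.6.3). A careful reader could derive both bounds with one division each.

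Most of that stands. The loss is not hidden, and a reader who infers that Section 8.6.1 contradicts Sections 8.1.3 and 8.5.1 goes further than the text. What remains is that disclosure neither reports nor bounds the all-dispensed rate.

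A reader might also infer that every exit for poor lens performance is an acuity failure, and hence that the reported rate must be too high. The documents do not support this. The term is not defined as acuity failure in the visible text. In Appendix D, the open category of refitting reasons reads "please specify, e.g., lens discomfort", so performance complaints need not concern acuity. Other exits need not either.

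For the same reason, coding particular exit reasons as non-response is not supported. There are practical obstacles too. Section 3.3.3 says "The Investigator should indicate the PRIMARY (one) reason that the subject was discontinued for each eye" and gives no rule for eyes whose reasons differ. Relatedness in Section 7.1.5 covers the study device and/or rewetting drops together, so it does not isolate the lens.

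Finally, effectiveness variables are redacted in Section 5.2, and the other effectiveness outcomes listed in the contents as Section 8.1.4 are not visible. The finding is therefore limited to visible text. The primary-analysis sentence, the missing-data rule and the sensitivity-analysis sentence are all readable.

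**Conclusion.** The point holds as a gap in reporting, not as an error or a concealed choice. Followed exactly, the plan yields a rate for evaluable subjects. That rate may differ from the all-dispensed rate, with overstatement plausible because of performance-related discontinuation. Neither sign nor size is fixed by the documents.

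On the assumed counts, the evaluable-only figure could exceed the all-dispensed rate by at most 9.0 points with 10.0% missing, 15.0 with 16.7% and 25.7 with 28.6%. It could fall short by 1.0 to 2.9 points if every missing subject would have succeeded. A reader might take 25.7 points as the likely bias. It is an extreme that needs both the full enrolment allowance lost after dispensing and failure of every missing subject.

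The one-eye rule is a genuine but minor flaw, worth 1.8 points per such subject in the 45/50 example.

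**What to change.** In Sections 8.6.1 and 8.6.8:

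1. Keep the current proportion, labelled evaluable-only. Beside it, report the proportion over all dispensed FAS subjects with worst-case (all missing = failure) and best-case (all missing = success) bounds, together with the number missing and the reasons.
2. Count a subject with an observed 3-Month eye worse than 20/40 as not achieving the both-eyes endpoint, even if the fellow eye is missing. That subject's status is known, so it counts as a failure in the best case as well.

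Exit Visit UDVA from early discontinuations may be shown as a separate supportive summary at its own time point. It should not stand in for the 3-Month value.

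The cost is some wording and a few table lines, with no new data collected. The drawback for the sponsor is that the lower bound will look less favourable than the evaluable-only figure.
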